#### Clinical assessments of late adverse effects

At annual visits for 10 years (from date of randomisation into study) physicians will record the development of breast shrinkage/distortion (including reconstructed breasts), breast induration (outside and inside tumour boost volume), breast pain and breast oedema (for patients receiving radiotherapy following breast conserving surgery) and telangiectasia (tumour boost site only), shoulder stiffness (compared with other side), ischaemic heart disease, rib fracture, costochondritis, symptomatic lung fibrosis, persistent cough and any other severe late event, including any specialist referral for investigation or management of late toxicity (for all patients).

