#### 10.1.2 Tumour bed boost

If a tumour bed boost dose is recommended, this needs to be declared before randomisation of each patient, together with the dose to be used. The dose prescription is either 10.0 Gy in 5 fractions or 16.0 Gy in 8 fractions to the 100% isodose, treating once-daily, and the boost must follow whole breast radiotherapy without a break. A boost is suggested for all patients under 40 years and for patients aged 40-49 years with either grade 3 tumours and/or lymphovascular invasion. A boost is also suggested for patients aged 50-59 years with one or more adverse prognostic factor, such as grade 3 tumours or lymphovascular invasion. There are no suggested indications for a boost in patients aged ≥60 years.

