#### Chest Wall Clinical Target Volume (CWCTV)

The clinical target volume encompasses the skin flaps and includes the soft tissues down to the deep fascia, excluding the underlying muscle and rib cage.

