Control group and treatment effects estimated separately. The inclusion of two test dose levels (Test 1 & 2) allows minor adjustment, for example by interpolation, between test dose levels to identify the fraction size most closely resembling the control schedule in terms of late change in breast/chest wall appearance and other adverse effects. The primary comparison is the rate of local tumour control at this 5-fraction dose level compared to the 15-fraction control. Since local relapse rates are so low, and no measurable difference in local relapse between the two test schedules is expected, interim analyses will also combine the test schedules for comparison with the control for the primary endpoint.

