## Incomplete repair during a 24-hour inter-fraction interval

Turesson showed that a 24-hour inter-fraction interval is more sparing of late damage (telangiectasia) than a 4-hour interval. The difference was equivalent to 11% difference in fraction size [3]. Estimates of recovery half-time ( $T_{1/2}$ ) for late endpoints in humans are based on the CHART head and neck trial:  $T_{1/2}$  for telangiectasia was 3.8 hours and for fibrosis was 4.4 hours [4]. It is likely that repair beyond a 24-hours is very limited, and that no adjustment is needed to fraction size when moving from a 7-day to 1-day inter-fraction interval. The 2-year results of the FAST pilot study raised no concerns that an inter-fraction interval of 2 or 3 days leads to excessive late effects [2]. The EQD2.8Gy of the 5-fraction regimen delivered as one fraction per week in the FAST trial was estimated to be 54 Gy, but no marked change in breast appearance at 2 years was recorded in any of 30 patients treated with 30 Gy in 5 fractions over 15 days [2].. An element of incomplete repair at 24 hours (relative to 7 days) after 4 out of 5 test group fractions might lead to an estimated 1% increase in NTE, as illustrated for Test group 1 below if the second, third, fourth and fifth fractions follow on consecutive days and each deliver 5.5 Gy of absorbed dose instead of prescribed 5.4 Gy.

		*∆NTE			
Fractionation regimen	$EQD_{2.8Gy}(Gy)$	(%)			
5.4 Gy x 1	9.2	-			
5.5 Gy x 4	38.0	-			
5.4 Gy x 1 plus 5.5 Gy x 4	47.2	-10			
** 5.4 Gy x 5	46.1	-11			
* Estimated NTE rates relative to 50 Gy in 25 fractions  ** Test group 2, assuming 100% repair between fractions					

Despite a lack of evidence suggesting need for dose modification taking account of incomplete repair and/or a lower  $\alpha/\beta$  value for late NTE than that estimated in the START A and FAST trials, a second test dose level (26.0 Gy in 5 fractions of 5.2 Gy) is included, as applied in START A. This allows interpolation, if required, in order to identify a 5-fraction schedule iso-effective with 40.05 Gy in 15 fractions.

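### The annual physician assessment, the only late-effect measure planned for every patient, names no late skin item outside the boost site and no skin or soft-tissue item for an unreconstructed chest wall

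*Protocol*

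**What the plan says.** Section 8.2.2 (Late reactions) sets an annual clinical assessment for all patients. Photographs and patient self-assessments are added for a subset. The paragraph on clinical assessments lists what physicians record each year for 10 years:

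- "breast shrinkage/distortion (including reconstructed breasts")
- "breast induration (outside and inside tumour boost volume")
- breast pain, then "breast oedema (for patients receiving radiotherapy following breast conserving surgery) and telangiectasia (tumour boost site only), shoulder stiffness (compared with other side")
- heart disease, rib fracture, costochondritis, lung fibrosis, cough, and an open item for any other severe late event or specialist referral for late toxicity, for all patients.

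Section 11.1 defines the chest-wall target: "The clinical target volume encompasses the skin flaps and includes the soft tissues down to the deep fascia". Section 12.2 allows bolus after mastectomy and not after breast conservation. Under section 10, a boost may be added only after breast conservation.

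**The concern.** The aim in section 3 covers safety as well as local control, and mastectomy patients are eligible. Section 17.2 plans time-to-event analyses of moderate or marked normal tissue effects. It would also match a five-fraction dose level to the control schedule "in terms of late change in breast/chest wall appearance and other adverse effects". Section 16.2 stops serious adverse event collection three months after treatment. Section 16.3 then sends unexpectedly severe late reactions, including late subcutaneous fibrosis, to the follow-up forms, so the annual form is the main route for late safety data.

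If that form has no named item for skin or soft tissue on an unreconstructed chest wall, a moderate or marked effect there that is not referred to a specialist has no place to be recorded by a physician. An analysis plan cannot recover data that were not collected. Telangiectasia is also not a marginal endpoint in this protocol: Appendix 2, in discussing incomplete repair, cites the finding that a "24-hour inter-fraction interval is more sparing of late damage (telangiectasia) than a 4-hour interval".

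**Working it through.** The point concerns which items are listed, so there is no stated figure to reproduce. The check sets the physician items of section 8.2.2 against the patient groups the protocol admits.

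| Physician item | Conserved breast, boosted | Conserved breast, no boost | Reconstructed (no implant) | Unreconstructed chest wall |
|---|---|---|---|---|
| Telangiectasia | boost site only | no | no | no |
| Shrinkage/distortion | yes | yes | yes | not named |
| Induration | inside and outside boost | yes | worded for the breast | not named |
| Pain, oedema | yes | yes | no | no |
| Shoulder, rib, costochondral, heart, lung, cough | yes | yes | yes | yes |
| Other severe late event or referral | yes | yes | yes | yes |

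Three things follow from the table.

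1. The restriction "telangiectasia (tumour boost site only") removes the only named skin item from unboosted breasts and from breast skin outside the boost. Because boosts follow breast conservation only, it removes the item from every mastectomy patient.
2. The last column has no named skin or soft-tissue item, although the skin flaps are inside that target. By contrast, the whole-breast target in section 11.1 starts 5 mm below the skin surface.
3. The unboosted group is unlikely to be negligible. Section 10.1.2 says: "There are no suggested indications for a boost in patients aged ≥60 years". Its size is not given.

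Next, what the other instruments add:

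- Photographs (section 8.2.2) score change in breast, reconstructed breast and chest-wall appearance, and distortion, on a three-point scale. They are taken at baseline and years 2, 5 and 10. The method still has to be validated in chest-wall patients.
- The quality-of-life booklet (Appendix 4, Measures) has items on change in skin appearance and on hardening. Appendix 4 counts symptoms scored in the top two categories as adverse effects.
- Neither instrument is limited by boost or surgery type, but section 8.2.2 limits both to a subset and section 9 starts both only after the first 150 patients.

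Planned coverage from section 17.3.3 and section 6.2: 3 × 732 = 2196; 2196 / 4000 = 54.9%; 4000 − 2196 = 1804 patients outside the sub-studies if these stop at their planned size. How many of those had a mastectomy or no boost cannot be derived from the protocol.

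**The case against.** The strongest case on the other side is that late skin and soft-tissue injury is measured elsewhere. A reader might infer from the physician list that unboosted and mastectomy patients have no graded skin endpoint at all. The protocol does not support that: photographs grade chest-wall appearance, and patients report skin change. Section 17.2's matching on chest-wall appearance corresponds to the photographic endpoint, so it is not contradicted.

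A reader might also infer that unreconstructed mastectomy patients yield no local late-effect data. That is wrong too. Shoulder stiffness, rib fracture, costochondritis and the severe-event item apply to them, and severe late fibrosis is meant to be picked up on the follow-up forms under section 16.3. Unboosted conserved breasts keep shrinkage, induration, pain and oedema. Appendix 2 also relies on fibrosis repair data and on breast appearance in a pilot study, not on telangiectasia alone.

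Restricting the breast-skin item may well be deliberate, given where the breast target begins. The case report form is not shown and may hold more items.

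All of this stands, and it limits the point. It does not remove it. The sub-studies cover a subset at a few time points. They provide no physician grading of telangiectasia or induration. The open item catches only severe or referred events. The argument about the depth of the breast target does not carry over to the chest wall.

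**Conclusion.** The point holds in a limited form. As section 8.2.2 is written, the trial would have little routine physician-graded evidence on late skin and subcutaneous injury after mastectomy without reconstruction, and no named physician skin item outside the boost site. It is a gap in the choice of items. It is not a contradiction or a wrong figure, and it does not touch the primary endpoint or the sample size.

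Its size can be stated only through coverage: graded appearance and skin data are planned for about 55% of patients, with up to 1804 outside that planned number. It is tempting to attach a loss of precision for telangiectasia, but that would need a boost rate and an event rate that the protocol does not give, so none is claimed. The conclusion assumes that the follow-up form mirrors section 8.2.2. If the form is wider, what remains is a mismatch of wording.

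**What to change.** In section 8.2.2 and on the annual follow-up form:

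- record telangiectasia for the whole treated breast or chest wall, separately inside and outside any boost volume, in the format already used for induration;
- reword induration, pain and oedema so that each covers the breast or the chest wall.

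If the case report form already carries these items, bring section 8.2.2 into line with it.

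The cost is a few extra fields at annual visits that already take place. Section 21.4 allows form items to be added without a protocol amendment and, where appropriate, collected retrospectively; the change to the wording of section 8.2.2 itself would go through the usual amendment route. The downsides are a slightly longer form and missing values for visits before the change, so the analysis of the new items would have to state from which visit they were collected.

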# Photographic assessments of late adverse effects (in all centres with local facilities)

Digital photographs will be taken at baseline (post-surgery but pre-RT) and at years 2, 5 and 10 after radiotherapy. Timing of assessments is based on experience from the START trial, with the aim to maximise the information collected whilst minimising the assessment burden. Two frontal views of the chest will be taken, one with hands on the hips and the other with hands raised as far as possible above the head. Both photographs will exclude the patient's head.

All photographs will be taken and retained locally in the first instance. Digital images will be coded and stored on a CD to be kept in a secure location. Periodically all CDs will be collected by ICR-CTSU and the images assessed blind by a select group of observers. Change in breast/reconstructed breast/chest wall appearance and distortion

compared with the post-surgical baseline will each be scored on a three-point graded scale. Breast size and surgical deficit will each be assessed on a three-point graded scale from the baseline photographs. Reliability and repeatability of the assessments will be verified. The feasibility of and procedures for this scoring mechanism have been established for breast conserving surgery patients in the START trial [15] and assessments for FAST-Forward will build on these existing methods, including validating the method in chest wall patients.

#### Patient self-assessments of late adverse effects (Quality of Life study)

Patients will be asked to complete self-assessments of quality of life at baseline, 3 and 6 months and 1, 2, 5 and 10 years after treatment. These will include the EORTC QLQ-C30 core questionnaire [16], the EORTC BR-23 Breast Cancer module [17], the Body Image Scale [18] and the Hospital Anxiety and Depression Scale (HADS) [19]. Of particular interest will be patient self-reporting of symptoms and impact on body image and functioning subscales. The aim will be to seek a patient-derived notion of 'radiation tolerance' that can be compared with physician and photographic endpoints, including interpolated estimates of isoeffect.

#### 9. FOLLOW-UP

After treatment clinical follow up should follow local guidelines.

For the purpose of the study, assessment of acute toxicities will be performed in the first 150 patients in the study. These will be undertaken weekly during treatment, for 4 weeks after treatment and weekly until the symptoms have reached RTOG≤1.

Follow up data will be collected annually for 10 years. Assessment of safety (late toxicities) and recurrence will be incorporated into the follow up visits.

Photographs will be taken from consenting patients at baseline and at 2, 5 and 10 years post randomisation.

Quality of Life booklets will be completed by consenting patients at baseline, 3 and 6 months and 1, 2, 5 and 10 years post randomisation.

Both of these studies will commence once 150 patients have been recruited into the trial.

#### 9.1 Withdrawal of Patients from Study Treatment and follow up

Patients who do not receive their allocated treatment for any reason should be treated at the discretion of their clinician. Unless the patient requests otherwise, all CRFs, including long term follow up, should be completed, regardless of treatment actually received. A trial deviation form should be completed to record details of deviation from treatment allocation. Analyses of all outcome data will be on the basis of intention to treat. As this is a non-inferiority trial if there is high non-compliance with the test treatment groups then an analysis of only those compliant with the protocol will also be conducted.

Patients are asked prior to randomisation to consent to follow up should they withdraw from the treatment allocation (see patient information sheet and consent form), and any patient unwilling to give that assurance prior to trial entry should not be randomised. Patients are however free to reverse that decision at any time without giving a reason. If a patient withdraws consent for further follow-up and for QL data to be collected, the appropriate form in the CRF should be completed and returned to ICR-CTSU. In the extremely unlikely event that the patient wishes to have their data removed from the trial completely the implications of this should be discussed with the patient to ensure that this is their intent and this should be recorded on the appropriate CRF form.

Should a patient become incapacitated at any point during the trial they will be withdrawn for their own protection. If this were to happen during the course of the patient's radiotherapy their treatment should be reviewed as a clinical decision by the Principal Investigator at their centre. No further trial procedures will be carried out and only data that is routinely collected i.e. disease status, vital status, cause of death will be used on behalf of the trial. Any samples already donated, i.e. blood and tissue, will be retained and used for the original research purpose. These procedures are fully explained in the patient information sheet, and patients are asked to consent to this prior to randomisation. A trial deviation form should be completed for any patient withdrawn from the trial for this reason.

# 9.2. Schedule of assessments

			Т	reatme	nt				Fo	llow-up	)			
Event	Prior to randomisation	Post randomisation pre RT	wk 1	wk 2	wk 3	Weekly to week 8	mth 3	mth 6	yr 1	yr 2	yr 3	yr 4	yr 5	yr 10
Eligibility checklist	х													
Informed consent	х													
Randomisation checklist	x													
Radiotherapy QA			Prior	to cent	re initia	ition and through	hout the	e trial re	ecruitm	ent pei	riod			
3D radiotherapy planning		х												
Radiotherapy treatment			х	x 	x 									
Radiotherapy verification				p to dai										
Serious Adverse Event (if applicable)			x	x	x	x	x							
Acute toxicity assessments		x (first 150 pts)	х	x	х	х								
Clinical assessment		x (first 150 pts)	x	x	х	x (first 150 pts)	х	х	x	х	х	х	х	x (Annually to yr 10)
Quality of life	x (baseline*)						х	х	х	x			х	х
Photographic assessment		х								х			х	х
Blood sample collection and family history questionnaire		At any time dur	ing the	trial, id	eally b	y the end of RT								
CT scan if recurrence		At the time of recurrence												
Tissue collection - 1° tumour - recurrence/new 1° tumour			As requested during the trial											

\* Follow up booklets will be sent by post from the ICR-CTSU office; Control group only; CRFs to be completed throughout the trial as indicated in the Trial Guidance Notes

#### 10. RADIOTHERAPY

Patients are randomised to 15 or 5 daily fractions (Fr) to the whole breast or post-mastectomy chest wall. A sequential tumour bed boost may be added after breast conservation surgery, but dose level (10.0 Gy or 16.0 Gy in 2.0 Gy Fr) must be declared before randomisation. Each patient will be allocated to one of the following groups:

Control: 40.05 Gy in 15 Fr of 2.67 Gy
Test 1: 27.0 Gy in 5 Fr of 5.4 Gy
Test 2: 26.0 Gy in 5 Fr of 5.2 Gy

# 10.1 Dose Prescriptions

#### 10.1.1 Whole breast/chest wall

Trial group	Total dose (Gy)	Dose per fraction (Gy)	Number of fractions	Fractions per week	Treatment time (weeks)
*Control	40.05	2.67	15	5	3
*Test group 1	27.0	5.4	5	5	1
*Test group 2	26.0	5.2	5	5	1

# Justification for choice of these regimens is found in Appendix 2

#### 10.1.2 Tumour bed boost

If a tumour bed boost dose is recommended, this needs to be declared before randomisation of each patient, together with the dose to be used. The dose prescription is either 10.0 Gy in 5 fractions or 16.0 Gy in 8 fractions to the 100% isodose, treating once-daily, and the boost must follow whole breast radiotherapy without a break. A boost is suggested for all patients under 40 years and for patients aged 40-49 years with either grade 3 tumours and/or lymphovascular invasion. A boost is also suggested for patients aged 50-59 years with one or more adverse prognostic factor, such as grade 3 tumours or lymphovascular invasion. There are no suggested indications for a boost in patients aged ≥60 years.

#### 11. RADIOTHERAPY TARGET VOLUMES, LOCALISATION AND OUTLINING

#### 11.1 Target Volume Definition

#### Whole Breast Clinical Target Volume (WBCTV)

This is based on the recommendations in the START trial protocol [20]. The CTV includes the soft tissues of the whole breast from 5 mm below the skin surface down to the deep fascia, excluding muscle and underlying rib cage.

#### Chest Wall Clinical Target Volume (CWCTV)

The clinical target volume encompasses the skin flaps and includes the soft tissues down to the deep fascia, excluding the underlying muscle and rib cage.

#### Tumour bed

Delineation of the tumour bed is recommended for all patients who had breast conserving surgery as this facilitates appropriate placement of the tangential breast field to maximise target coverage whilst and minimising dose to organs at risk (OAR). Examples are shown in the planning pack.

To assist the delineation, it is strongly advised that titanium clips or gold seeds are implanted into the walls of the tumour excision cavity (tumour bed) at the time of breast conserving surgery as per British Association of Surgical Oncology (BASO) guidelines [21]. The tumour bed may be localised if there is a well-defined seroma in the absence of implanted markers. Either of these localisation methods will be necessary if the boost radiotherapy is to be delivered with a conformal photon plan.

#### Planning Target Volumes (PTV)

A margin should be added to whole breast and tumour cavity CTV, taking into account set-up error, breast swelling and breathing; a typical PTV margin is 10 mm for both whole breast and tumour bed. A field-based whole breast PTV can be used and this method is illustrated in the planning pack.

#### Organs at Risk (OAR)

It is mandatory to contour ipsilateral lung and heart for dose volume histogram assessment. The heart should be outlined from the inferior aspect above the diaphragm, to the superior aspect below the pulmonary arch. Volumes are recorded for the purposes of the trial.

#### 11.2 Patient Position

The patient must lie supine in a stable and reproducible position. The same position must remain for simulation, CT scanning and treatment. An immobilisation device, such as a breast board with arm and wrist supports, an arm pole and/or vac-fix bag should be used. Ideally, the immobilisation should allow daily reproducibility of +/- 5 mm. The patient must not be moved between tangential fields.

#### 11.3 Acquisition of Outlines

A full 3D set of outlines covering the whole breast and the organs at risk must be collected with a slice separation of no more than 5 mm. The imaging technology to be used must be x-ray CT only to provide accurate dose-volume histogram (DVH) data for plan assessment.

#### 12. RADIOTHERAPY PLANNING

It is compulsory to outline target volumes and the relevant organs at risk for radiotherapy planning of FAST-Forward patients. All computer planning must be carried out on a 3D dataset, and correction for tissue heterogeneity must be applied. Usually, a tangential pair beam arrangement is used to encompass the whole breast PTV, minimising the ipsilateral lung and heart in the fields. The treatment plan must be optimised with 3D dose compensation aiming to fulfil the criteria in Table 2 below.

